## Objective

This study examines static/dynamic balance performance, daily activities, and confidence in less fear of falling for people with Parkinson's disease (PD) performing in-home balance exercises with a smartphone-based wearable telerehabilitation system (intervention group). Twenty-two subjects with idiopathic PD will be potentially recruited.

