## Study Design

The experimental design will include laboratory assessments (i.e., pre-assessment baseline at the beginning of week 1, post-assessment at the end of week 6, and retention-assessment 1 month after week 6) and in-home balance exercises. Participants will perform in-home balance exercises (3 days per week for 6 consecutive weeks) with the Smarter Balance System (SBS).

Laboratory assessments: Subjects will be quantitatively assessed for static/dynamic balance performance using a measure for the range of limits of stability (LOS) in both anterior-posterior (A/P) and medial-lateral (M/L) directions. After completion of the pre-assessment, a member of the research team will train all participants to use the SBS's smartphone, and all participants will be additionally trained in the use of the custom belt and the walker and multimodal biofeedback for in-home dynamic weight-shifting balance exercises (WSBE) guided by the SBS. After completion of the post-assessment, all participants will complete a usability and acceptability questionnaire (UAQ) for the SBS.

In-home balance exercises: All participants will use the SBSs for 6 consecutive weeks, and they will complete in-home WSBE (i.e., physical therapists' recommended dynamic balance exercises) with the SBS (3 days per week) in both A/P and M/L directions. All participants will perform in-home dynamic WSBE by standing inside a walker (no wheels). The instructional video provided by the SBS will show how to perform dynamic WSBE in both A/P and M/L directions by standing inside the walker without touching or holding onto it unless the subject experiences loss of balance. After each trial, the SBS's smartphone app will store exercise-related data.

Performance metrics: Measured data from the SBSs will be analyzed using MATLAB (The MathWorks, USA). Statistical analysis will be performed using SPSS (IBM Corp., Armonk, NY, USA). As a function of the pre/post/retention-assessments, two primary outcome measures (range of LOS) will be used to evaluate static/dynamic balance performance. Ranges of LOS in degrees correspond to the furthest deviations of the body tilt in both A/P and M/L directions. The UAQ score (Likert scale) will be used to assess the usability and acceptability of the SBS, and the participants' compliance with the in-home balance training regimens, total exercise time, and number of completed exercises will be quantitatively analyzed.

Name	Time Frame	Brief Description

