Range of limits of stability	Pre-assessment (baseline at the beginning of week 1), post-assessment (at the end of week 6), and retention-assessment (1 month after week 6)	Limit of stability refers to the outermost range in anterior-posterior and medial-lateral directions at which the subject can lean from the vertical without changing the base of support.
Usability and acceptability questionnaire (UAQ)	Post-assessment (at the end of week 6)	The UAQ is a self-reported questionnaire used by subjects to assess the usability and acceptability of the proposed SBS.

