## Statistical Analysis Plan

The primary outcome measure for evaluating balance performance is the range of Limits of Stability (LOS) in both the anterior-posterior (A/P) and medial-lateral (M/L) directions. LOS represents the maximum angular excursion that a participant can achieve while maintaining a stable base of support without stepping or losing balance. LOS will be measured at three time points: baseline (Week 1, prior to intervention), post-intervention (Week 6), and retention (Week 10, one month after the intervention ends). These measurements will be obtained using the SBS smartphone application, which quantifies participants' dynamic balance capacity by analyzing trunk sway and range of controlled movement.

To assess the efficacy of the SBS-guided intervention, Repeated Measures Analysis of Variance (ANOVA) will be used with time (baseline, post, retention) as a within-subject factor and group (intervention vs. control) as a between-subjects factor. Main effects of time and group, as well as the interaction effect (time  $\times$  group), will be evaluated to determine whether balance performance improved differentially over time depending on the assigned intervention. A significant interaction effect would suggest that the SBS system had a unique impact on improving LOS relative to the paper-based control regimen.

As a measure of user experience and technology acceptance, the Usability and Acceptability Questionnaire (UAQ) will be administered at the post-assessment time point (end of Week 6). The UAQ consists of self-reported Likert-scale items that evaluate perceived ease of use, clarity of instructions, comfort of the wearable system, motivation to exercise, and willingness to continue using the SBS. Responses will be summarized using descriptive statistics (mean, standard deviation) for each item. Between-group differences in total UAQ scores will be analyzed using independent samples t-tests to determine whether the intervention group rated the SBS as more usable and acceptable than the paper-based regimen.

All analyses will be conducted using IBM SPSS Statistics v29 (IBM Corp., Armonk, NY, USA), with the significance level set at  $\alpha = 0.05$ .

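### The planned between-group t-test on total UAQ scores fails whether the study has one arm or two, and the design and the SAP disagree on which it is

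*Combined protocol and SAP*

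**What the plan says.** The Objective names one group, labelled as the intervention group, and gives one number: "Twenty-two subjects with idiopathic PD will be potentially recruited". No split by group is given.

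Under Study Design, the paragraph on in-home exercises states "All participants will use the SBSs for 6 consecutive weeks". The paragraph on laboratory assessments states that after the post-assessment "all participants will complete a usability and acceptability questionnaire (UAQ) for the SBS". The outcome table in the same section defines the UAQ as a "self-reported questionnaire used by subjects to assess the usability and acceptability of the proposed SBS". None of these sections describes a paper-based regimen, a control group or an allocation step.

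The Statistical Analysis Plan section assumes two groups. It puts a group factor (intervention versus control) into the repeated measures ANOVA for limits of stability (LOS) and names a paper-based comparator. For the UAQ it lists five domains: ease of use, clarity of instructions, and then "comfort of the wearable system, motivation to exercise, and willingness to continue using the SBS". It plans a mean and SD for each item, and then an independent-samples t-test on the total score "to determine whether the intervention group rated the SBS as more usable and acceptable than the paper-based regimen".

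**The concern.** A two-sample test needs two samples measured on the same scale. The Study Design supplies one sample. If the SAP is right and a second sample exists, the scale is still a rating of a device that the second group would not have used.

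The t-test is the only inferential analysis planned for the UAQ, and the UAQ is one of two outcomes in the outcome table. It is also the only place where the total score is used, because the descriptive summaries are by item. If the test cannot be run or interpreted, the total has no usable analysis. A forced comparison could report a difference that reflects which items people were able to answer and not how usable they found their regimen.

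**Working it through.** The plan gives no power, effect size, SD or sample-size derivation for the UAQ, so there is no figure to reproduce. The check takes each reading of the design in turn.

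**Reading A: one arm, as in the Study Design.** All 22 planned participants use and rate the SBS, so n1 = 22 and n2 = 0. The t statistic divides the difference in means by s_p × √(1/n1 + 1/n2). With n2 = 0 there is no second mean and 1/n2 is undefined. Running the test on 22 simulated scores against an empty sample returned no value for the statistic, the p-value or the degrees of freedom.

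What can be estimated is the mean total among SBS users. The 95% confidence interval half-width, in SD units, is t(0.975, n − 1)/√n:

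- n = 22 (all respond): 2.080/4.690 = 0.443 SD
- n = 18 (assumed, 4 lost): 2.110/4.243 = 0.497 SD
- n = 15 (assumed, 7 lost): 2.145/3.873 = 0.554 SD

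**Reading B: a paper arm exists, as in the SAP.** The five listed domains, judged by their wording:

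| Domain | Applies to a paper-only user? |
|---|---|
| Ease of use | Only if worded for the paper regimen |
| Clarity of instructions | Only if worded for the paper regimen |
| Comfort of the wearable system | No |
| Motivation to exercise | Only if worded for the paper regimen |
| Willingness to continue using the SBS | No |

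Two of five (40%) cannot apply, and the other three apply only if reworded. The totals in the two arms would therefore be built from different content.

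**Direction of any bias under Reading B.** The documents do not say whether the total is a sum or an average, or how unanswered items are handled. As an illustration, assume one item per domain, paper users leave the two SBS items blank, and everyone scores the three shared items 4.

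- Sum, blanks counted as zero, SBS users also give 4 on the two SBS items: SBS 5 × 4 = 20, paper 3 × 4 = 12. The 8-point gap favours the SBS with no difference on shared content.
- Mean of answered items, same responses: SBS 20/5 = 4, paper 12/3 = 4. No gap.
- Mean of answered items, SBS users give 3 on the two SBS items: SBS (3 × 4 + 2 × 3)/5 = 18/5 = 3.6, paper 4. The gap favours paper.
- Complete cases only: no paper participant has a total, and the second sample is empty again.

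The size and sign of the contrast follow the scoring rule. The lack of comparability does not depend on it.

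**The case against.** The strongest reply is that the SAP plainly expects a control group: it names a between-subjects group factor, an assigned intervention and a paper-based comparator, and the Objective's label of intervention group hints at one too. That stands. A reader might infer from the Study Design that there is no second group as a matter of fact. The documents do not support that, because they contradict each other and do not say which section governs. Reading A is therefore conditional, and its cause is shared with the LOS ANOVA. Reading B is specific to the UAQ: adding a control arm to the design would repair the ANOVA but not this test.

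A second reply is that paper users might receive a version worded for their regimen. Such an instrument, or a score limited to shared items, would answer Reading B. Neither is described, and the outcome table defines the instrument as one "used by subjects to assess the usability and acceptability of the proposed SBS".

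A reader might also infer that the comparison would necessarily flatter the SBS. That does not follow, since total scoring and the handling of unanswered items are unstated and the sign can go either way.

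Finally, the UAQ is not the primary outcome, and the planned item means and SDs survive under both readings. That is correct and limits the damage. Those means and SDs also allow item-level intervals to be worked out, so what is missing is a valid analysis of the total.

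**Conclusion.** The design and the SAP disagree on whether a second group exists, and the planned t-test on total UAQ scores is invalid under both readings. With one arm it is 22 versus 0 and cannot be computed. With a paper arm, at least 2 of 5 listed domains do not apply to that arm, and the totals do not measure the same thing.

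This rests on the explicit statements about all participants in the Study Design and on the domain wording in the SAP. The items themselves are not in the document, so the count of two is by domain description. The 0.44 SD half-width describes the precision of the one-arm alternative. It assumes that all 22 are recruited and respond, and the recruitment figure is itself stated as potential.

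**What to change.** 1. **Settle the number of arms first**, and make the Objective, Study Design, outcome table and Statistical Analysis Plan agree. The same decision determines whether the LOS ANOVA keeps its group factor and interaction. Deleting the UAQ test alone would leave the contradiction in place.

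2. **If single-arm:** delete the between-group UAQ t-test. Report the mean total UAQ among SBS users with a 95% confidence interval and the number responding, alongside the item summaries already planned. The cost is SAP wording only, with no new data.

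3. **If a paper arm is confirmed:** describe it in the Objective and Study Design, including how participants are allocated, how many are in each arm and which questionnaire each arm completes. Restrict the between-group comparison to a named set of items that both arms can answer, worded for each regimen. Summarise SBS-specific items in the SBS arm only. This costs more than SAP wording: the design text and the UAQ description change, and a paper-regimen version may be needed before the Week 6 post-assessment.

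4. **In either case**, state how the UAQ score is formed (sum or item mean) and how unanswered items are handled.
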